4. STUDY DESIGN

This study is a 6-month, post-market, prospective, randomized, multicenter, bilateral, open-label, cross-over, comparative clinical investigation.

The study will be conducted at up to 7 sites in the U.S.A. Approximately 140 subjects will be randomized and bilaterally implanted, to achieve approximately 110 evaluable subjects (55 in the study arm and 55 in the control arm). Subjects are to be treated on both eyes by LipiFlow and to be implanted bilaterally with the Symphony IOLs.

JUSTIFICATION OF STUDY DESIGN

The study is to be conducted in USA as a post-market study. The study is designed to evaluate improvements in biometry reliability, visual outcomes and refractive outcomes after LipiFlow treatment versus an active control group and, through a cross-over design, to evaluate visual and refractive outcomes after postoperative LipiFlow treatment. The study design allows evaluation of preoperative and postoperative LipiFlow treatments on cataract surgery outcomes.

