10. EXPERIMENTAL PLAN

10.1 OVERVIEW

This study will be conducted in accordance with U.S. Code of Federal Regulations, the Declaration of Helsinki, ISO 14155 and all other applicable laws and regulations. The study will not begin until IRB approvals have been obtained.

This study will be a post-market, prospective, multicenter, bilateral, randomized, open-label, cross-over, comparative clinical study conducted at up to 7 sites in the U.S. Approximately 140 subjects will be randomized and bilaterally implanted, resulting in approximately 110 evaluable subjects (55 in the study arm and 55 in the control arm).

After signing the informed consent, subjects meeting all inclusion and exclusion criteria will be randomized to either the Study group or the Control group.

The duration of study participation is from the initial Preoperative Visit #1 to a final visit at 3 months or 4 months after the second-eye cataract surgery, depending upon the subject's randomized group assignment. All subjects in both arms are intended to have bilateral cataract surgery. The subjects randomized to Study group will undergo preoperative LipiFlow treatment and the subjects randomized to Control group will not receive preoperative LipiFlow treatment. Three months postoperatively, both groups will be evaluated for clinical outcomes and the Control group will receive LipiFlow treatment as the cross-over group. The Control group will be evaluated at 4 months postoperative for clinical outcomes.

Key data collection for all subjects/eyes includes distance visual acuities, manifest refraction, contrast acuity, keratometry, biometry, corneal topography, visual symptoms, Meibomian gland evaluation, biomicroscopic slit-lamp findings, complications and adverse events. A chart summary of all examination or treatment procedures required at each study visit is provided in **Appendix B**. If needed, specific equipment necessary to perform the required procedures will be supplied for the duration of the study (**Appendix C**). The study visit schedule is described in Section 10.2.

Although the study is not masked, to maintain consistency, it is recommended that a single individual (study technician or coordinator designated by the investigator) conduct all study-related vision testing, although a back-up person should also be designated and trained.

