10.2 VISIT SCHEDULE

The study visit schedule for all study subjects is outlined in **Table 1**.

Subjects randomized to the **Study Group** will undergo a minimum of the following four study visits (with visit windows shown in parentheses):

- 1) Preoperative Visit #1, including LipiFlow treatment (may occur on the same day or within 1 week of Visit #1)
- 2) Preoperative Visit #2 (2 - 4 weeks after LipiFlow treatment)
- 3) 1 Month Postop (30 - 60 days after cataract surgery on second eye)
- 4) 3 Months Postop (10 to 14 weeks after cataract surgery on second eye)

Subjects randomized to the **Control group** will undergo a minimum of the following five study visits (with visit windows shown in parentheses):

- 1) Preoperative Visit #1
- 2) Preoperative Visit #2 (2 - 4 weeks after Preoperative Visit #1)
- 3) 1 Month Postop (30-60 days after cataract surgery on second eye)
- 4) 3 Months Postop (10 to 14 weeks after cataract surgery on second eye), including the crossover LipiFlow treatment, which should occur within 0 - 7 days after the 3 months postoperative visit
- 5) 4 Months Postop (4 to 6 weeks after receiving crossover LipiFlow treatment)

Unscheduled visits may be conducted as necessary at the discretion of the investigator for medically-indicated follow-up.

Table 1: Visit Schedule

NAME OF VISIT	GROUPS	PROCEDURES	VISIT WINDOW
Preoperative #1	All	Informed Consent, Screening, Baseline, Randomization and Enrollment	Per site practice
LipiFlow Treatment	Study Group	LipiFlow treatment	LipiFlow treatment can occur on the same day or within 1 week of Visit #1
Preoperative #2	All	Preoperative	Study Group: 2-4 weeks after LipiFlow treatment; Control Group: 2-4 weeks after Visit #1
1 Month Postop	All	1 month postoperative	30-60 days after cataract surgery on second eye
3 Months Postop	All	3 months postoperative; The crossover Control group will receive LipiFlow treatment within 0-7 days after the 3 months postoperative visit	10 to 14 weeks after cataract surgery on second eye
4 Months Postop	Crossover Control Group Only	4 months postoperative	4 to 6 weeks after receiving crossover LipiFlow treatment

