The subjective ocular / visual symptoms are to be assessed at the designated visits by asking "Are you having any difficulties with your eyes/vision?" Subjects should not be prompted for specific responses; however, if a subject complains of halos, glare or starbursts, the severity should be determined (mild, moderate or severe).

PRVSQ QUESTIONNAIRE

The PRVSQ questionnaire is to be assessed at the designated visits. Subjects will be prompted for specific responses, including halos, night glare or starbursts.

MEDICATIONS

Postoperative medications should be used as is customary for each investigator and recorded in the source document for each subject. Medications will be recorded on each postoperative case report form as applicable.

ADVERSE EVENTS

Subjects should be assessed at each visit for occurrence of and/or change in status of any adverse events, particularly serious and/or device-related adverse events.

See Section 11.0, Adverse Events, for further information.

ADDITIONAL PROCEDURES AT DESIGNATED POSTOPERATIVE VISIT(S):

- Eyelid margin evaluation for each eye
- TBUT for each eye
- Ocular surface staining for each eye
- Ocular and systemic medications

Crossover LipiFlow Treatment (Only for Control Group)

The crossover LipiFlow treatment is only applicable to and required for the subjects in the Control group. It will be performed on the Control group subjects on the same day or within 1 week of the 3-month postoperative visit, after all study examination procedures are completed. If the subject has an active ocular adverse event or other contraindications to LipiFlow treatment, the LipiFlow treatment should not be performed at this visit.

The LipiFlow treatment should be performed per the LipiFlow System Instructions for Use.

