APPENDIX A DIAGRAM OF STUDY FLOW

APPENDIX B SUMMARY OF PROCEDURES REQUIRED AT EACH VISIT

Examination	Preop Visit #1	LF Tx ^d (Study Group Only)	Preop Visit #2 ^e	Operative	1-Mo. Post-op	3-Mo. Post-op and Crossover LF Tx ^f	4-Mo. Post-op (Crossover Group Only)
Informed consent, medical and ocular history, inclusion/exclusion criteria	X						
Potential visual acuity, targeted refraction, IOL power calculations, corneal topography	X		X				
IOL power/serial number, Toric power/axis (if needed)				X			
Monocular UCDVA, BCDVA	X ^c				X	X	X
Binocular UCDVA, BCDVA					X	X	X
Binocular UCIVA and UCNVA						X	X
Manifest refraction	X ^c				X	X	X
Contrast acuity testing (binocular, 10% contrast acuity and 20/40 contrast threshold)						X	X
Keratometry, biometry (repeat 3 sets of biometry / keratometry measurements)	X		X				
Meibomian gland assessment	X				X	X	X
Ocular surface staining	X		X		X		
TBUT	X		X		X		
Eyelid margin evaluation	X		X		X		
Meibomian gland imaging (LipiScan or LipiView II)	X				X		X
Biomicroscopic slit-lamp exam ^a	X	X	X		X	X	X
Fundus exam ^b	X						
Adverse events	X	X	X		X	X	X
Ocular and systemic medications	X	X	X		X	X	X
Ocular/Visual symptom assessment (non-directed)	X		X		X	X	X
SPEED and PRVSQ questionnaires	X		X			X	X

^a Includes determination of medical and lens findings/complications, lens orientation. Slit-lamp exam is performed both before and after LipiFlow treatment.

^b Fundus exam may be performed dilated with ophthalmoscopy or undilated per site practice standard of care.

^c Preoperative UCDVA, BCDVA and refraction tests will be performed per site practice standard of care.

^d Preoperative LipiFlow treatment can occur the same day or within 1 week of Preoperative Visit #1.

^e Preoperative Visit #2 will be 2-4 weeks after LipiFlow treatment for study group and be 2-4 weeks after the Preoperative Visit #1 for control group.

^f LipiFlow treatment after 3 months postop exams for the Crossover Control group only.

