#### 2.2 VISIT WINDOWS

Each randomized group will have two preoperative visits, 1 month postoperative visit and 3 months postoperative visit. Subjects randomized to study group will receive LipiFlow treatment before the second preoperative visit. Subjects randomized to control group will receive crossover LipiFlow treatment after 3 months postoperative visit. There will be a 4 months postoperative visit for control group subjects. The exact number of days for each interval is described in the protocol. The number of eyes with missing visits or data outside of the visit intervals will be reported.

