### 4.2.3 ENDPOINTS EVALUATED AT 4-MONTH POSTOPERATIVE FOR CONTROL GROUP SUBJECTS ONLY

Mean change in LogMAR monocular BCDVA and UCDVA and mean change in LogMAR binocular UCDVA, UCIVA, UCNVA, BCDVA and contrast acuity will be reported for control group eyes from 3 months to 4 months postoperative visit. Better visual acuity outcomes (lower mean LogMAR scores) at 4 months visit are expected.

Mean MRSE at 4 months postoperative will be compared to target MRSE. Frequency and percent of eyes with MRSE within 0.50 D and within 1.00 D of target MRSE at 4 months postoperative will be reported.

Version 1.0 5 SAP/DRYE-102-SELF

Mean change in total Meibomian gland score and mean change in total SPEED score from 3 months to 4 months postoperative will be reported. An increase in both mean total Meibomian gland score and mean total SPEED are expected.

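### The 3- to 4-month change in controls has no concurrent untreated comparator, so the cross-over cannot evaluate postoperative LipiFlow as Protocol Section 4 says

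*Protocol*

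**What the plan says.** The justification in Protocol Section 4 says the study is designed, "through a cross-over design, to evaluate visual and refractive outcomes after postoperative LipiFlow treatment", and concludes: "The study design allows evaluation of preoperative and postoperative LipiFlow treatments on cataract surgery outcomes".

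The operational sections describe delayed treatment of one arm:

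- Protocol 10.6: "The crossover LipiFlow treatment is only applicable to and required for the subjects in the Control group".
- Protocol 10.2 gives controls a fifth visit, "4 Months Postop (4 to 6 weeks after receiving crossover LipiFlow treatment"). The Study group list has no counterpart.
- Protocol Appendix B labels that column "4-Mo. Post-op (Crossover Group Only"), and SAP 2.2 agrees: "There will be a 4 months postoperative visit for control group subjects".
- Protocol 10.1 ends participation at "a final visit at 3 months or 4 months after the second-eye cataract surgery", according to arm.

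SAP 4.2.3 reports controls' changes from 3 to 4 months in acuity, contrast acuity, gland score and SPEED, and compares 4-month MRSE with target. It states a direction for acuity: "Better visual acuity outcomes (lower mean LogMAR scores) at 4 months visit are expected". SAP Appendix I lists means, SDs and 95% confidence intervals. Neither document names a comparator for this period, uses the pre-crossover trend, or warns about time effects.

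**The concern.** The term cross-over usually implies that treated and untreated periods can be compared within subjects while time effects are balanced between sequences. Here one arm switches in one direction, and no group is observed without new treatment between the 3- and 4-month visits. The change therefore combines any LipiFlow effect with whatever else moves over those weeks: late postoperative change, familiarity with the tests, and expectation in an unmasked study.

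What is at stake is the reading of the 4-month results. Section 4 says the design evaluates postoperative treatment, and SAP 4.2.3 expects improvement. An interval excluding zero on the favourable side could then be presented as evidence for postoperative LipiFlow, which this comparison cannot supply.

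**Working it through.** **1. The plan's own figures.** The documents give no power, test or success criterion for the 3- to 4-month change. The only sample-size figure concerns the randomized 3-month UCDVA comparison (Protocol 20.5, SAP 5): 55 per group, a 1-line difference, SD 1.6 lines.

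- Enrolment: 55 / (1 − 0.20) = 68.75, so 69 per group. This reproduces.
- Power: noncentrality 1 / (1.6 × √(2/55)) = 3.28 on 108 df gives 94.7% at the stated one-sided 0.05 and 90.1% at two-sided 0.05. The mismatch in sidedness is a separate matter.

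Only 55 and 1.6 are borrowed below.

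**2. Who is observed when** (windows from Protocol 10.2, weeks after second-eye surgery).

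| | Study group | Control group |
|---|---|---|
| 3-month visit | weeks 10–14 | weeks 10–14 |
| Crossover treatment | none | 0–7 days later |
| 4-month visit | none | weeks 14–21 (10 + 0 + 4 to 14 + 1 + 6) |

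No Study group visit is scheduled after week 14, so the post-crossover period has no concurrent comparator of any kind.

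**3. What pre-crossover information exists** (Protocol Appendix B).

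| Outcome | 1 month | 3 months | 4 months |
|---|---|---|---|
| Monocular and binocular UCDVA, BCDVA | yes | yes | yes |
| Manifest refraction (MRSE) | yes | yes | yes |
| Meibomian gland score | yes | yes | yes |
| SPEED, UCIVA, UCNVA, contrast acuity | no | yes | yes |

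For the first three rows, the controls' untreated 1- to 3-month change is already collected. Two details in the SAP matter here. MRSE at 4 months is compared with target only; no 3- to 4-month change is planned. Appendix I also lists the 4-month SPEED and gland-score changes as from baseline, whereas 4.2.3 says from 3 months. A change from baseline would also span the cataract surgery.

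**4. Illustration of what drift could do.** Assume no LipiFlow effect, n = 55 and a natural drift of d SDs of the change. The chance that the 95% interval lies wholly on the improvement side is the upper tail of a noncentral t (54 df, 2.5% critical point) with noncentrality d√55:

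- d = 0 gives 2.5%
- d = 0.1 gives 10.9%
- d = 0.2 gives 30.7%
- d = 0.3 gives 58.9%

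By symmetry, adverse drift of the same size gives the same chance of an interval wholly on the worsening side.

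To put this in lines, let the SD of the change be 1.6 × √(2(1 − ρ)), with ρ the assumed within-person correlation. At ρ = 0.8 it is 1.6 × √0.4 = 1.012 lines, the standard error is 1.012/√55 = 0.136, and the half-width is 0.274 line.

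| Drift (lines) | ρ = 0.5 | ρ = 0.7 | ρ = 0.8 | ρ = 0.9 |
|---|---|---|---|---|
| 0.2 | 15% | 22% | 30% | 53% |
| 0.3 | 28% | 42% | 58% | 86% |
| 0.5 | 62% | 84% | 95% | >99% |

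SAP Appendix II uses 50 letters per LogMAR unit, so with a line of 0.1 LogMAR, 0.2 line is one letter. A concurrent untreated group sharing the same drift would hold the figure at 2.5% whatever the drift. The calculation is per subject. Monocular, MRSE and gland outcomes are tabulated by eye, and treating paired eyes as independent would narrow the intervals.

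**5. How far the 1- to 3-month change can help.** The 1-month window is days 30–60 and the 3-month window is days 70–98. The gap can therefore run from 70 − 60 = 10 days to 98 − 30 = 68 days. The 3- to 4-month gap runs from 28 to 7 + 42 = 49 days. Scaling a 10-day change to 4 weeks multiplies it, and its measurement error, by 28/10 = 2.8. If recovery slows with time, subtracting the earlier slope removes too much and biases against LipiFlow. The earlier change is useful context but does not replace a control.

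**The case against.** The best defence is that the SAP already treats these items modestly. They are among the other endpoints, confined to controls and reported without test, alpha or success criterion. The one-way structure is disclosed throughout. The first Section 4 statement can be read as purely temporal, the clinical hypothesis names no crossover effect, and the background gives the purpose as treatment before surgery. Appendix I already tabulates controls' acuity by line over time, so some trend will be visible. All of this stands and limits the weight of the point. It does not rescue the second Section 4 statement, which says the design allows postoperative treatment to be evaluated on surgical outcomes.

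A reader might go further and infer that ordinary recovery will be credited to LipiFlow. The documents do not support that. They give no figure for change after weeks 10–14, and drift could be adverse: Section 10.6 recommends leaving any Nd:YAG capsulotomy until after study completion, and the background describes MGD as chronic. The M&S System randomizes letter presentation (Appendix O), which removes chart memorization, though not general familiarity with the test. The percentages above follow from assumed drift and do not estimate what will happen.

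A reader might also infer that the crossover weakens the main results. It does not: every randomized comparison is made at or before the 3-month visit, ahead of the crossover treatment.

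**Conclusion.** The point holds as a mismatch between claim and design. Section 4 attributes to the cross-over a property it lacks: the 3- to 4-month result is an uncontrolled, open-label before-after change in one arm. A LipiFlow effect cannot be separated from time, retest or expectation effects.

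The size and direction of any resulting bias are unknown. The 11%, 31% and 59% figures show only that modest drift would be enough to mislead; they rest on assumed drift, 55 evaluable controls at 4 months and one observation per subject, and the version in lines also rests on the assumed correlation. Because the affected items are secondary and descriptive, this is a correction worth making before results are written up, and it does not threaten the trial's primary conclusion.

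**What to change.** - **Protocol Section 4 and SAP 4.2.3:** describe the 4-month results as an uncontrolled before-after description in the Control group, and remove the statement that the design evaluates postoperative LipiFlow on outcomes.
- **SAP 4.2.3 and Appendix I:** for monocular and binocular UCDVA and BCDVA, MRSE and gland score, tabulate the controls' untreated 1- to 3-month change, with its 95% confidence interval and the actual visit intervals, beside the 3- to 4-month change. Label it descriptive context. This includes adding the 3- to 4-month MRSE change, which is not now planned.
- **Any difference in change per unit of time:** at most a sensitivity analysis, stated to assume steady drift.
- **SPEED, UCIVA, UCNVA and contrast acuity:** keep purely descriptive, since they have no 1-month value.
- **Appendix I:** reconcile the from-baseline labels for 4-month SPEED and gland score with SAP 4.2.3 in the same edit.

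The cost is wording, one extra table from data already scheduled, and a more modest claim. No visit, procedure or subject is added. The table does not remove expectation effects and offers nothing for SPEED, the symptom outcome plausibly most exposed to them.

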5. ACRONYMS

The following acronyms are used throughout the document:

- ACD: Anterior Chamber Depth
- AL: Axial Length
- BCDVA: Best Corrected Distance Visual Acuity
- D: Diopters
- IOL: Intraocular Lens
- MGD: Meibomian Gland Dysfunction
- MGE: Meibomian Gland Evaluator
- MGYLS: Meibomian Glands Yielding Liquid Secretion
- MR: Manifest Refraction
- MRC: Manifest Refractive Cylinder
- MRS: Manifest Refractive Sphere
- MRSE: Manifest Refraction Spherical Equivalent
- SPEED: Standard Patient Evaluation of Eye Dryness
- TBUT: Tear Break-up Time
- UCDVA: Uncorrected Distance Visual Acuity
- UCIVA: Uncorrected Intermediate Visual Acuity
- UCNVA: Uncorrected Near Visual Acuity

6. STUDY OBJECTIVES AND ENDPOINTS

The purpose of this study is to evaluate the LipiFlow treatment in adult patients with mild to moderate meibomian gland dysfunction (MGD) undergoing bilateral cataract surgery in terms of preoperative surgical planning and postoperative outcomes including refractive outcomes, visual outcomes and ocular comfort.

6.1 KEY STUDY ENDPOINTS

- MEAN MONOCULAR UCDVA AT 3 MONTHS POSTOPERATIVE IN THE STUDY AND CONTROL GROUPS
 - Success criteria: Statistically significantly lower mean LogMAR UCDVA is expected in the study group eyes compared to control group eyes at 3 months postoperative.
- PRECISION (STANDARD DEVIATION) OF PREOPERATIVE AL, ACD, AND KERATOMETRIC MEASUREMENTS (K) FOR THE STUDY AND THE CONTROL GROUP
 - AL, ACD and K values will have three sets of measurements at the Preoperative Visit #1 and again at the Preoperative Visit #2. For AL, ACD and keratometry, the standard deviation of each set of measurements will be computed at both preoperative visits, and the average of the three computed standard deviations from each preoperative visit is defined as the precision. The difference in precision between the two preoperative visits will be calculated for AL, ACD and K values. The precisions of the AL, ACD and keratometry measurements are expected to be better (smaller standard deviation) for study group eyes than the ones for control group eyes.
- RATE OF REFRACTIVE PREDICTABILITY AT 3 MONTHS POSTOPERATIVE FOR THE STUDY AND CONTROL GROUPS
 - The frequency, proportion and 95% confidence intervals of eyes with achieved MRSE within 0.50 D and 1.00 D of targeted MRSE will be summarized at 3 months postoperatively. The proportion of study group eyes with achieved MRSE within 0.50 D and within 1.00 D of targeted MRSE is expected to be greater compared to control group eyes.
- RATE OF BOTHERSOME OCULAR SYMPTOMS AT 3 MONTHS POSTOPERATIVE FOR THE STUDY AND CONTROL GROUPS
 - The rate of directed reports of bothersome ocular symptoms (halos, night glare, starburst, and night vision difficulties) at 3 months postoperatively is expected to be lower for study group eyes than that for control group eyes.

- MEAN CHANGE IN TOTAL MEIBOMIAN GLAND SCORE IN THE STUDY GROUP COMPARED TO THE CONTROL GROUP FROM BASELINE TO 1 MONTH POSTOPERATIVE
 - Change in total Meibomian gland score is defined as total Meibomian gland score at 1 month postoperative minus the score at Baseline (before LipiFlow treatment). Greater mean change in total Meibomian gland score is expected for study group eyes than that for control group eyes.

6.2 OTHER ENDPOINTS

- 1-Month Postoperative Visit:
 - Mean change in Number of Meibomian Glands Yielding Liquid Secretion (MGYLS) from Baseline visit to 1 month postoperative in the Study group compared to the Control group.
 - Mean change in ocular surface stain grade from Baseline visit to 1 month postoperative in the Study group compared to the Control group.
 - Mean change in Tear Break-up Time (TBUT) from Baseline visit to 1 month postoperative in the Study group compared to the Control group.
 - Mean change in Eyelid Margin Evaluation from Baseline visit to 1 month postoperative in the Study group compared to the Control group.
- 3-Month Postoperative Visit:
 - Mean monocular BCDVA in the Study group at 3 months postoperative compared to the Control group.
 - Mean binocular UCDVA and BCDVA in the Study group at 3 months postoperative compared to the Control group.
 - Mean binocular UCIVA in the Study group at 3 months postoperative compared to the control.
 - Mean binocular UCNVA in the Study group at 3 months postoperative compared to the Control group.
 - Mean manifest refraction spherical equivalent (MRSE) at 3 months postoperative compared to target MRSE in the Study group compared to the Control group.
 - Contrast acuity in the Study group at 3 months postoperative compared to the Control group.
 - Mean change in total Standard Patient Evaluation of Eye Dryness (SPEED) score from Baseline visit to 3 months postoperative in the Study group compared to the Control group.
 - Mean change in total meibomian gland score in the Study group compared to the Control group from Baseline to 3 months postoperative.

- Control Group 4-Months Postoperative Visit:
 - Mean change in monocular UCDVA and BCDVA from 3 months to 4 months postoperative.
 - Mean change in binocular UCDVA and BCDVA from 3 months to 4 months postoperative
 - Mean change in binocular UCIVA from 3 months to 4 months postoperative
 - Mean change in binocular UCNVA from 3 months to 4 months postoperative
 - Mean MRSE at 4 months postoperative compared to target MRSE
 - Percent of eyes with MRSE within 0.50 D and within 1.00 D of target MRSE at 4 months postoperative
 - Contrast acuity at 4 months postoperative compared to 3-month.
 - Mean change in total meibomian gland score from 3 months to 4 months postoperative.
 - Mean change in total SPEED score from 3 months to 4 months postoperative.
- Rate of adverse events in the Study and Control groups.
- Rates of medical and/or lens findings in the Study and Control groups.

